 Focus Groups	 Randomization	 Double-Blind
 Control Group	 Placebo	 Withhold/Delay Treatment
 Specimen Collection	 Deception	 Telephone Survey
 Other (Describe)		

2.2. Describe how randomization or other treatment assignment will be made.

Randomization will occur on a 1:1 basis to one of the two study conditions (iCBT or usual care) using a permuted block randomization with randomly varying block sizes of 2, 4 and 6 and stratification by gender (because females with schizophrenia have a better course and may respond better to traditional CBT). The study biostatistician will generate randomization lists based on the above procedure. The encrypted randomization file will be located on a server (i.e., \\VHAPHIFPCMIRECC\Research Studies\[name] -Integrated CBT to Improve Work) that is not accessible to the study personnel who make subject contact during the randomization procedure. S/He will access the file and provide the randomization token. S/He will not have subject contact nor know which condition is being assigned. Further, s/he does not have a stake in the outcome of the study.

2.3. For retrospective research studies, provide the "look-back" period. (e.g., December 1, 1999 through December 31, 2008.) **Not Applicable.**

3. Study Duration

3.1. Provide the estimated length of time to enroll all subjects and complete the study. **To allow that not all identified patients will qualify and not all qualifying patients will elect to participate, we will conduct more baseline screenings than required. We propose, accordingly, to consent to the baseline assessment 48 patients in the first year of the study (months 6 to 12), 96 patients in the second year (months 13 to 24), and 48 patients in the third year (months 25 to 30), producing 24 randomized patients in year 1, 48 in year 2, and 24 in year 3, for an estimated total of 96 randomized subjects (48 per group). All 96 subjects will be randomized by middle of the third year. Data collection will be complete after the middle of the fourth year.**

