9.4. Request Waiver of Documentation of Informed Consent

9.5. List the title of the key personnel involved in the following activities:

9.5.1. **Person Obtaining Consent**

9.5.1.1. Provide the title(s) of individual(s) **Principal Investigator, Co-Investigator, Research Coordinator, Supported Employment Specialists, Independent Assessors**

9.5.1.2. Type of training received to perform this process: All Staff: **HIPAA, GCP, and Human Subjects Protection Training. The research coordinator will attend the Research Coordinator training class offered by the Research Compliance Officer prior to engaging in research activities.**

9.5.2. **Pre-Recruitment Screening** (the use of medical records and other data bases to determine populations and individuals eligible for the study), **Not Applicable**

9.5.3. **Recruitment Process** (the process in which individuals are contacted and first introduced to the study and to the possibility of participating as subjects), **Principal Investigator, Co-Investigators, Research Coordinator, Supported Employment Specialists, Independent Assessors**

9.5.4. **Informed Consent Process** (the process by which recruited subjects are fully informed about participating in the study and then formally give their voluntary consent for participating), **Principal Investigator, Co-Investigator, Research Coordinator, Supported Employment Specialists, Independent Assessors**

9.5.5. **Screening of Recruited Subjects** (those activities in the protocol in which a final determination of eligibility of prospective subjects is made during the early phases of the study, using laboratory data, inclusion and exclusion criteria, and other person-specific information), **Principal Investigator, Co-Investigator, Research Coordinator**

9.5.6. Include the breakdown of each individual's responsibilities:

9.5.6.1. Principal Investigator, **Oversee the entire study design, implementation, and data collection. He will also provide clinical and diagnostic guidance.**

9.5.6.2. Co-Investigator, **[name] will provide all the CBT trainings and monitor for fidelity and reliability. He will oversee training on structured interviews, questionnaires and oversee reliability. He will provide clinical and diagnostic guidance. Our TBD biostatistician will analyze all the data. S/he will also maintain the randomization key.**

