We will assess residuals in the longitudinal linear random effects model with normal QQ plots and estimation of the skewness and kurtosis coefficients. If these are coefficients exceed their classical cut-offs of 3 and the QQ plots confirm skewness and/or kurtosis, we will then perform a longitudinal analysis based on a random effects generalized linear model with a gamma error distribution (with SAS Proc GLIMMIX) that handles skewed and kurtotic distributions. We will fit such a model with identity link function (linear mean model), such that the resulting estimates and tests are comparable to those of the normal error random effects model. We will compare the estimates and p-values. If the two approaches agree with respect to significance at the specified alpha level, then we will use the results from the linear random effects model with normal error. If they disagree we will base results on the gamma error distribution model.

Prior to each hierarchical analysis, baseline outcomes, pre-treatment assessment scores, and demographics (except gender which by definition is balanced due to be a stratification factor in the randomization) will be compared between the two treatments at the two-sided alpha = .05 level. Any significant baseline variables will be included as covariates in the hierarchical regression models. We will also perform as a sensitivity analysis based on an adjustment of the ITT models for post-randomization confounding due to differences in medication patterns between the randomized groups. Such adjustments will be based on a causal modeling approach that distinguishes between direct effects of the iCBT intervention, on the one hand, and differences in medication patterns, on the other, using randomization and its products with baseline covariates as the instrumental variables to control for unmeasured confounding due to choice of medication.

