While the present study is designed to minimize lost observations, the proposed random effects or hierarchical regression approach is superior to last observation carried forward in minimizing bias and Type 1 error and inferentially equivalent to multiple imputation.⁷⁹ To assess the sensitivity of treatment effect estimates to missing data, we will compare the results under the above hierarchical regression models with those based on shared parameter models that account for informative missingness that is dependent on unobserved outcomes through a latent variable.⁸⁰ If the results between the two approaches are similar then we will present the proposed hierarchical regression models as robust to informative missing data; otherwise we will note that the results may be

sensitive to informative missing data and augment them with those based on the shared parameter model.

(ii) **Work outcome.** The primary trial outcome measure, workforce participation (composite index) at 6, 12 and 18 months analyzed in the manner described above. A significant ITT difference on the total WBI score across 6 and 12 months would support the hypothesis that iCBT is more efficacious than usual care at improving work outcomes by the end of treatment (Primary Aim 1). Similarly, WBI score at 18 months is a secondary outcome, and a separate ITT effect on work outcomes at 18 months with the respective month-treatment interaction in favor of iCBT would support the hypothesis that it promotes better work outcomes than usual care during the 6 months after the completion of treatment (Secondary Aim 2).

(iii) **Functional outcome.** The second trial outcome measures include the Work Behavior Inventory and the total score on the Specific Levels of Functioning Inventory (SLOF) at 12 months A significant ITT difference on the WBI and the total SLOF score across 6, 12 months would support the hypothesis that ICBT is more efficacious than usual care at improving functioning by the end of treatment (Secondary Aim 1). Similarly, WBI and SLOF total score at 18 months is a secondary outcome, and the separate ITT effects on functioning at 18 months with the respective month-treatment interaction in favor of iCBT would support the hypothesis that it promotes better functioning than usual care during the 6 months after the completion of treatment (Secondary Aim 3).

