5.1.1. Data Use/Transfer Agreement YES NO N/A

5.1.2. Off-Site Storage/Transfer of Research Data YES NO N/A

5.1.3. Memorandum of Understanding YES NO N/A

5.1.4. *(Note: VA data disclosed to a non-VA investigator at an academic affiliate for research purposes needs to be approved by the Under Secretary of Health or designee.)*

6. List who is to have access to the data and how they are to access it (anyone who has access to the data is responsible for its security). **The following members will have access to the data: The PI ([name]), the RC, the Co-investigator ([name]), the SES, the Independent Assessors, the Counseling Psychotherapist Supervisor ([name]), the SE Consultant ([name]), the co-investigator ([name]) and the study biostatistician (TBD). They can access the hard copies kept in the MIRECC, as well as the electronic copies on the secure server. Our study consultant, [name], will not have access to any study data.**

7. Describe who is to have access and be responsible for the security of the information (e.g., the Coordinating Center, the statistician, and PI who has ultimate responsibility). **The following members are responsible for the security of the data: The PI ([name]), the RC, the independent assessors, the supported employment specialists, the Co-investigator ([name]), the Counseling Psychotherapist Supervisor, the SE Consultant, the co-investigator, and the study biostatistician (TBD).**

8. Provide mechanisms used to account for the information. **Only the above-named study staff will have access to the information.**

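### The plan says the person releasing allocations does not know the condition, but on the plain reading that person is the biostatistician who writes the list, keeps the key and analyses the data

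*Combined protocol and SAP*

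**What the plan says.** Item M.2.2 sets out the allocation procedure. On the list: "The study biostatistician will generate randomization lists based on the above procedure". The encrypted file is kept on a server "that is not accessible to the study personnel who make subject contact during the randomization procedure". The text then turns to one unnamed individual: "S/He will access the file and provide the randomization token", followed by "S/He will not have subject contact nor know which condition is being assigned". That individual is also said to have no stake in the result.

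The staff responsibilities in R.9.5.6.2 state: "Our TBD biostatistician will analyze all the data. S/he will also maintain the randomization key". The data-access list in Y.6 names "the study biostatistician (TBD" once, and X.6 likewise lists a single study biostatistician.

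Masking is stated for the independent assessors (M.3.2, O.1.1 and R.9.5.6.4). Nothing is said about masking the analyst, and the double-blind box in M.2.1 is not ticked.

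**The concern.** M.2.2 presents ignorance of the assigned condition as a property of the person who hands out allocations. Read with R.9.5.6.2, one role appears to write the list, release from it, keep the key and analyse every outcome. A person in that position can look up any allocation, so the property cannot be guaranteed.

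The consequence lies in the analysis more than in enrolment. Usual care involves no study group, so treatment is open to participants and therapists, and some decisions about the primary outcome are still unwritten. If the person who settles them can tell which arm is which, the choices cannot be shown to be independent of the arms, and nothing in the plan protects against that.

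**Working it through.** The plan gives no figure to reproduce and no arithmetic applies. The check sets the role descriptions side by side.

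**1. Who does what**
- Generates the list: the study biostatistician (M.2.2).
- Releases each token: an unnamed individual (M.2.2). The sentence before the pronoun mentions only a file and study personnel in the plural. The only single person introduced earlier in the item is the biostatistician.
- Keeps the key: the biostatistician (R.9.5.6.2).
- Analyses the data: the biostatistician (R.9.5.6.2).
- Same role under both labels: R.9.5.6.2 calls the biostatistician TBD, M.2.2 says study biostatistician, and Y.6 joins the two. No second statistician is named.

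**2. Two readings of the pronoun**
- If it means the biostatistician, M.2.2 contradicts itself and R.9.5.6.2. The author of the list and holder of the key can identify all 96 allocations (48 per group).
- If it means someone else who passes on a coded token, that person could be unaware of the condition. But no such person is identified anywhere, and the biostatistician still generates, holds and analyses.

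On either reading M.2.2 needs correcting.

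**3. Decisions still open to the analyst**
- *Composite.* It is one of the primary indices in section K and the primary outcome in W.4.1 and W.4.2(ii). No scoring or weighting is given.
- *Type of job attainment.* W.4.2(i) assigns logistic, log-linear and linear models to binary, count and continuous outcomes. Job attainment is described as instances in K, as timing in O.2.1.1 and as jobs attained in O.2.2, so which model it receives is not settled.
- *Error distribution.* W.4.2(i) requires skewness or kurtosis coefficients above 3 and then that "the QQ plots confirm skewness and/or kurtosis". The coefficients are numeric; the confirmation is visual. After that the rule is fixed: normal model if the two agree on significance, gamma model if they do not.
- *Missing data.* The wording "If the results between the two approaches are similar" carries no threshold, but the hierarchical results are reported either way. The judgement affects only the robustness statement and whether shared-parameter results are added.

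The discretion that can reach a main estimate is therefore the construction of the composite, the typing of job attainment and the QQ-plot confirmation.

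**4. What coded arms would hide**
Swapping labels A and B does not change whether two models agree on significance, nor which baseline variables differ at .05. It hides only the direction of the effect.

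**The case against.** The strongest reply is that the sentence in M.2.2 concerns the moment of assignment. Its purpose is concealment from the staff who enrol participants, and M.2.2 supports that with encryption and a restriction on access. The biostatistician's overlapping roles do not break it. The pronoun has no explicit antecedent, so the text may be unclear rather than false. The analysis rules are also tighter than they first appear: there is a numeric cut-off of 3, a fixed normal-or-gamma rule, model families tied to outcome type, and a missing-data comparison that never replaces the main model. The deeper weakness is the undefined composite, which calls for pre-specification whoever holds the list.

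Most of this stands, and it limits the point. Three stronger readings are tempting and are not supported:
- A reader might infer that the trial's masking as a whole does not exist. The role overlap does not touch the blinding of the independent assessors.
- A reader might infer that the plan promises a masked analyst and breaks the promise, or that analysis choices will be made with the arms in view. The documents are silent on analyst masking and do not say the key will be used during analysis. They show only that the analyst could identify the arms.
- A reader might infer that enrolling staff can see the list, because M.2.2 gives the randomization file the same server folder as the code key (X.1.3.1) and study data (Y.1). M.2.2 states that the file is encrypted and closed to staff with participant contact during randomization, so failed concealment does not follow.

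What the reply does not remove is that the sentence cannot be true of the biostatistician and that no other releaser is named.

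**Conclusion.** The concern holds in a limited form. The statement that the releaser does not know the condition cannot hold for the biostatistician, who on the plain reading is the releaser. No separate releaser and no masked analyst is described. This rests on taking the pronoun to refer to the biostatistician and on TBD and study biostatistician being one role. If the first assumption is wrong, the fault becomes an unnamed releaser, and the overlap of list, key and analysis remains.

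The size of any bias cannot be derived from the documents. Sample size, alpha and power are unaffected. The practical weight comes from the unscored primary composite and a small number of judgement steps, which would be settled by someone able to identify the arms. It is a worthwhile and inexpensive correction; it is not evidence that the trial's results would be biased.

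**What to change.** - Have an existing staff member hold the list and key and release the tokens. That person should be confirmed to have no participant contact and no analysis role. A DMU administrator may be a candidate, but R.9.5.6.4 describes only server support and access to coded data, so lack of participant contact would have to be checked.
- Give the biostatistician data with arms coded A/B and without the treatment-group tracking data listed in Y.3, which would reveal the arms. Release the code only after the composite's scoring, the covariates and the model choices (including the type of job attainment and the QQ-plot criterion) are fixed in writing. The planned baseline comparisons and model checks can all be run on A/B labels.
- Rewrite M.2.2 to say who generates, who holds, who releases and who analyses, and what each of them knows. Bring R.9.5.6.2 into line.

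The cost is a little more data handling, training one person to release tokens, and a few sentences of text. Because A/B coding hides only the direction of the effect, it supplements fixing these choices in writing and does not replace it.

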4.3. Provide all relevant information about the drug

- 4.4. Explain any wash-out periods, rescue medications permitted and any type of medications not permitted while enrolled in the study.
- 4.5. Describe blinding and un-blinding procedures.
- 4.6. Include the dosage, route of administration, previous use, and the safety and efficacy information on any drug used for research purposes.
- 4.7. Describe rationale for the dosage in this study.
- 4.8. Justify why the risks are reasonable in relation to anticipated benefits and/or knowledge.

- 4.9. Describe where drug preparation will be done.
- 4.10. All drugs for CMCVAMC subjects must be dispensed through the VA investigational pharmacy.
- 4.11. Describe where the study treatment will be administered.
- 4.12. Describe plan for tracking a non-compliant treatment study subject.
- 4.13. Summarize any pre-clinical data.
- 4.14. Describe the process for the storage, security, dispensing and return of an investigational drug.

5. **Investigational Device** (If not applicable state, "Not Applicable.") **Not Applicable.**
 - 5.1. The Investigational Device Exemption (IDE) number must be submitted for all significant risk devices and if an IDE exists for a non-significant device.
 - 5.2. Significant Risk or Non-significant Risk - If a device is not approved by the FDA, specify whether or not the sponsor has determined this device to be a "significant risk" or "non-significant risk" as defined by the FDA.
 - 5.3. Provide all relevant information about the device.
 - 5.4. Describe blinding and un-blinding procedures.
 - 5.5. Specify if device is:
 - 5.5.1. FDA approved
 - 5.5.2. Used for off-label purposes
 - 5.5.3. Not yet FDA approved.
 - 5.6. Explain if the investigational device will be delivered and/or stored by the Principal Investigator or Pharmacy Services.
 - 5.7. Describe the process for the storage, security, dispensing and return of an investigational device.
 - 5.8. For research involving an investigational device, describe the SOP or plan for device control.
 - 5.9. Address how the device will be stored in such a way that only research staff associated with the protocol will have access to the device.
 - 5.10. Describe measures that will be put into place to ensure that the device will only be used in participants of this research protocol.

N. Does this project involve international research? YES NO

1. *For further instructions refer to [VHA Directive 2005-050](#), Requirements for Conducting VA-Approved International Research Involving Human Subjects, Human Biological Specimens, or Human Data*
2. *VHA Handbook 1200.05 definition of international research - VA international research is any VA-approved research conducted at international sites (not within the United States (U.S.), its territories, or Commonwealths); any VA-approved research using either human biological specimens (identified, de-identified, or coded) or human data (identified, de-identified, or coded) originating from international sites; or any VA-approved research sending such specimens or data out of the U.S. (see par. 56). NOTE: For the purposes of this Handbook, research conducted at U.S. military bases, ships, or embassies is not considered international research.*

O. Study Procedure

1. Study Procedures

1.1. Outline all study procedures - (*If necessary, include a table or flow chart, showing the schedule of the procedures and interactions. Distinguish between interventions that are experimental and carried out for research purposes vs. those that are considered standard of care. Routine procedures that are performed solely for research purposes should also be identified.*)

Consenting patients will be administered a baseline assessment battery (diagnostic, work outcomes, functional outcomes, symptom, neurocognitive, and attitude measures) to determine eligibility. Baseline assessment procedures will take approximately 4-5 hours. (Please see section O.2.1 for full descriptions of the assessment battery.) Subjects will be notified of their eligibility status for the treatment component of the research by phone within 2 weeks of their baseline assessment.

The research team will seek permission to obtain the contact information of a secondary contact person, to assist in maintaining contact with the veteran over the course of the 18 active months of the study. Though participants will be encouraged to provide this information, they may refuse to do so and still remain in the study. The research team will not disclose any information to this secondary contact person.

Eligible subjects who give a second informed consent will be randomly assigned to receive either iCBT or to usual care. All randomized participants will enter into supportive employment at the CMCVAMC. iCBT will be delivered as a group therapy for 12 months of weekly or biweekly sessions (see below). iCBT sessions will take approximately 1 hour. Blind, reliable independent assessors will reassess participants every 6 months after participants begin treatment groups over an 18-month participation period, producing mid-treatment (6 month) end-of-treatment (12 month), and post-treatment (18 month) assessments. Follow-up assessment procedures will take approximately 3-4 hours. The Research Coordinator will conduct a 15-minute Check-In at baseline to gather information about medications and services being received outside of this research study; the Supported Employment Specialists or Independent Assessors will conduct the 15-minute Check-In every 3 months after participants begin treatment groups (i.e., at 3-, 6-, 9-, 12-, 15-, and 18-months). The SE Specialists will also conduct the assessment of employment variables at these Check-Ins using the Workforce Participation form using an informal interview assisted by the use of a calendar and review of holidays and other activity anchors, supplemented by the ongoing assessment they conduct as part of the SE activities.

We are proposing a prospective randomized controlled trial with participants recruited from the CMCVAMC. We will randomize 96 patients (48 patients per condition). Independent assessors will be blinded to participant treatment group allocation. Assessment sessions will occur at baseline, and at 6, 12, and 18 months after therapy groups begin; brief check-ins will occur at each assessment session, and also at months 3, 9, and 15 after therapy groups begin.

Subjects in the iCBT condition will receive weekly or twice weekly group sessions for 12 months. iCBT follows a treatment manual developed by Perivoliotis, Grant, & Beck. The manual details the approach (engagement, behavioral activation, cognitive remediation/restructuring, maintenance) and individualized treatment planning. It also describes strategies and techniques to deal with positive and negative symptoms, mood symptoms, and suicidality. Included in these strategies are mindfulness exercises, designed to assist the participant in identifying feelings and biological processes that accompany a stimulus (i.e.,

food and/or drink). It incorporates cognitive remediation strategies. iCBT sessions will be video recorded, for purposes of quality control and supervision.

Subjects in both conditions will participate in the existing SE program at CMCVAMC.

All participants will continue to receive any services (medical, psychiatric, case management) they were already receiving.

The primary outcome measure will be the work participation indices, including 1) instances of job attainment, 2) average days worked per week while employed, 3) average number of hours worked per week while employed, 3) total weeks worked, and 4) a composite of these indices. Secondary outcomes measures will be total score of the Work Behavior Inventory (WBI) at the 6, 12, and 18 month follow up and the total score on the Specific Levels of Functioning scale (SLOF) measured at post-treatment 6, 12, and 18month follow-up.

Treatment conditions

Usual Care - Usual care will entail continued access to all treatments available to all Veterans receiving treatment at the CMC VAMC Mental Health Clinical without restriction.

iCBT - Subjects in the iCBT condition will receive sessions of group therapy scheduled at least once every week for up to 12 months following randomization. iCBT will follow a treatment manual developed by Perivoliotis, Grant, & Beck⁷⁴ based upon conceptualizations developed in Schizophrenia: Cognitive Theory, Research, and Therapy.²¹ The manual details the modular approach (engagement, behavioral activation, maintenance) and individualized treatment planning. It also explains in detail strategies and techniques for negative symptoms, hallucinations, delusions, anxiety, depression, and suicidality. It also gives guidelines for when and how to incorporate the UCLA social skills role-plays³⁷ and cognitive remediation strategies.⁷⁵ The employment specialists will be masters level clinicians and will provide the iCBT. iCBT sessions will be video recorded, for purposes of quality control and supervision.

- i. Cognitive remediation - Cognitive remediation refers to programs that target specific cognitive domains and aim to improve them, often through thousands of repetitions of the same task, an approach called "drill and practice."³⁸ There is substantial evidence that cognitive remediation significantly improves performance on cognitive batteries in people with schizophrenia³⁹, and (perhaps by extension) improves measures of functioning. Several recent meta-analyses of cognitive remediation programs have found moderate effect sizes for improvement in cognitive functioning⁴⁰, social cognitive functioning,⁴¹ and psychosocial functioning.⁴⁰ Kurtz conducted a literature review of studies that reported neurocognitive data in the context of different psychosocial interventions. He concluded that global cognition, and attention, memory, and problem-solving domains, were associated with outcome variables in people with schizophrenia enrolled in vocational rehabilitation programs.⁴² Five randomized control trials have been conducted integrating cognitive remediation and vocational rehabilitation. McGurk et al. reviewed 4 of the 5 trials in a 2008 review article, and subsequently published the results of another trial. In her review, and in the 2009 trial, she concluded that the combination of cognitive remediation and vocational rehabilitation improved both cognitive functioning and vocational rehabilitation outcomes.^{43, 44}

The cognitive remediation program we will use, Brain HQ by Posit Science (https://portal.brainhq.com/?study=best_vet), is a series of computer “games” developed by neuroscientists to target particular areas of cognition, for instance verbal and visuo-spatial memory, working memory, sustained attention, set-shifting, planning and problem solving, and others. The program is designed to provide practice on these cognitive areas in the form of interactive and engaging computer games. Brain HQ software is commercially available and targeted at a healthy adult population looking to improve cognitive skills that are already within the normal range of performance. It has also been developed for clinical populations with a unique training set for people with schizophrenia, and it has programs with more gradual increases in challenge level, less emphasis on timed tests, and a new interface for facilitators working with patients.

The cognitive remediation module lasts 4 months. During this module, participants will meet twice weekly for hour-long sessions. 40 minutes of those sessions will be devoted to computerized cognitive remediation using Brain HQ. The cognitive domains practiced by the subjects will be individually tailored to the areas of greatest cognitive weakness of each subject. During the cognitive reappraisal portion (see below), the challenges and gains of the subjects using Brain HQ will be discussed and the relationship of the skills mastered to employment situations will be discussed. The employment specialists will perform the cognitive remediation. Consistent with cognitive remediation programs already in place at CMCVAMC, the Brain HQ patient kiosk is connected to the local network, and provides access to the Internet; patients will be monitored by the Supported Employment Specialist during computer use. The name, email address, and password requested when logging on this site will be that of the Supported Employment Specialist (SES), who will then enter a subject code for each subject. Thus no identifiable information about the subject is being entered for use of this computer program.

- ii. **Cognitive reappraisal skills.** During the cognitive remediation and cognitive reappraisal module, participants will meet twice weekly. The cognitive reappraisal portion will occur 10 minutes prior and 10 minutes after cognitive remediation. The difficulties and gains encountered during cognitive remediation will be discussed. In particular, cognitive restructuring will be conducted around expectancies and attitudes that might block goal achievement. This will involve training patients to *recognize negative automatic thoughts* (“I can’t do it,” “I do not have the energy), to *identify thinking errors* (e.g., emotion based reasoning such as “if it feels like I can’t do it, then I can’t do it”), and to *generate alternative explanations* to specific unhelpful or inaccurate thoughts and beliefs. All skills are taught in a fun and engaging manner.

March 2016 Amendment

This protocol was initially submitted with a study objective to evaluate whether iCBT vs. Psychoeducation (PE) can improve engagement and success in an existing SE program among the most functionally disabled patients with schizophrenia.

We decided to change the control group from Psychoeducation (PE) to usual care. We made this change because experts in randomized clinical trials (RCT) design have recently argued that control condition that is “active” in an effort to

equalize the attention association with the experimental intervention can reduce the power of the design to detect that impact of the intervention.⁸⁷ Thus, a control condition that is also active may lead to biasing the study against detecting a difference compared to the experimental group. Psychoeducation is often used as a minimally active control condition in lieu of usual care. Unfortunately, psychoeducation has been demonstrated to reduce relapse, reduce and shorten hospital admissions, and improve medication compliance⁷⁶. It is an active comparator to iCBT, given its significant improvements in areas related to functional outcome. Again, this may in fact reduce the ability to detect a positive impact of iCBT.

This study change was approved by the Sponsor (See Request for Administrative Modification of a Rehabilitation Research and Development Service (RR&D) Project form signed by [name], Director, RR&D)

Plans for subjects already enrolled in the study: Prior to this change in the control arm, we were in the initial stages of existing participants who have been randomized and remain active (3 iCBT group, 3 Psychoeducation group). Since the Psychoeducation participants expect a group, will offer all these participants the iCBT group. Because those two participants who had been randomized to the Psychoeducation group would be offered the iCBT outside the original design, their data will be excluded from data analysis. They will otherwise receive all the benefits of the study.

All existing consented and randomized participants will be re-consented describing the new design just specified, with a usual care arm (that does not involve any group treatment). Again, those participants who want to participate in a group treatment (or an additional group if they are in iCBT arm), have the treatment resources of the Mental Health Clinic that they can access outside of their involvement in this study.

Supported Employment (SE). SE is the standard clinical intervention that is offered to Veterans with severe mental illness. Therefore, SE is not a research intervention. However, the supported employment specialists will be a part of the research team. Subjects randomized to either treatment group (i.e., iCBT, usual care) will participate in SE. All participants will also continue receive psychiatric care. Case management will continue for subjects already receiving such services. The SE program will adhere to the IPS model adopted by the CMCVAMC in 2005 as part of a national initiative (see Background, above). The IPS model has been well described¹⁸ and training occurs through a mentor-trainer model. Multiple studies have demonstrated the importance of high fidelity scores on SE program evaluation in terms of employment outcomes⁷⁷.

1.2. Explain if and how the follow-up of subjects will occur. The baseline assessment is designed to: a) determine baseline levels of work functioning, psychosocial functioning, symptomatology, cognitive impairment, and dysfunctional belief endorsement, and b) determine whether participants are eligible for the treatment phase of the study.

The research team will strive to form treatment groups as quickly as possible. However, it may take several weeks to accumulate enough eligible and willing participants to form a treatment group (i.e., 6-8 participants). The intention of the follow-up assessments and check-ins is to measure the impact of treatment on the study measures. Therefore, the follow-ups and check-ins are tied to the beginning of the treatment groups.

All participants who are eligible and consent to randomization will participate in three additional assessment sessions. The mid-treatment and post-treatment assessments are designed to measure change from baseline that occurred during the treatment period and will consist of a re-administration of the baseline measures. The follow-up assessment occurs 6 months after the end of the treatment period (18 months after treatment groups begin). The Research Coordinator will conduct the 15-minute check-in at baseline; the Supported Employment Specialists or Independent Assessors will conduct the check-in every 3 months after treatment groups begin (i.e., at 3-, 6-, 9-, 12-, 15-, and 18-months).

1.3. Describe where, how and who will be conducting study procedures. The primary purpose of the follow-up assessments is to determine the durability of change post-treatment. Table 1 depicts the study assessment timetable. Baseline study assessments will be carried out by the study Research Coordinator, while follow-up assessments will be carried out by the Independent Assessors. The Research Coordinator will conduct the 15-minute check-in at baseline; the Supported Employment Specialists or Independent Assessors will conduct the check-in every 3 months after treatment groups begin (i.e., at 3-, 6-, 9-, 12-, 15-, and 18-months).

Table 1: Assessment measures and administration timeline

Measure	Baseline	3 Month (after groups begin)	6 Month (after groups begin; mid treatment)	9 Month (after groups begin)	12 Month (after groups begin; end of groups)	15 Month (after groups begin; post groups)	18 Month (after groups begin; post group follow up)
SCID	X		-		-		-
WHODAS	X		-		-		-
Work Readiness	X						
Risk Assessment	X						
Data from WBI	X		X		X		X
SLOF	X		X		X		X
BNSS	X		X		X		X
SAPS	X		X		X		X
DAS	X		X		X		X
ABS	X		X		X		X
BSES-SF	X		X		X		X
QOLI	X		X		X		X
BCIS	X		X		X		X
CNB	X		X		X		X
B-CATS	X		X		X		X
UPSA	X		X		X		X
Check-in	X	X	X	X	X	X	X
Workforce Participation	X	X	X	X	X	X	X
			Note. "X" = measure administered				

1.4. If a survey study, specify the estimated amount of time that subjects will need to complete the questionnaires/tools. The baseline assessment will take approximately 4-5 hours. The follow-up assessments will take approximately 3-4 hours. The check-ins will take approximately 15 minutes.

1.5. If a blood draw, specify the amount of blood to be drawn in milliliters and in teaspoonfuls or tablespoonfuls and specify how often and where the blood will be drawn. **Not Applicable.**

2. **Data Collection** (Include all questionnaires and survey tools with the submission.)

